4.2.4. Analysis Visiting Windows

No analysis visit window will be defined for urodynamic data, and questionnaire data. Nominal clinical visits will be used for summary and analysis. Any unscheduled data will be listed only.

Diary data used for analyses will be windowed as follows:

1. For baseline, the 3-day diary completed closest to study drug administration will be used regardless of when the diary is completed within the screening and randomization period.
2. For post-baseline the analysis visit windowing will be based on the scheduled visit dates relative to the study drug administration date according to the schedule of assessments in the protocol instead of the actual visit dates. This is set up to take into account the visit delays due to COVID-19 should it happen. Table below provides details on the target study day and corresponding visit windowing rules for the post-baseline visits.

Table 2: Diary Data Analysis Visit Window Slotting

Analysis Visit	Target Study Day	Range	Visit Window
Week 2	15	15 ± 7 days	[8, 22]
Week 6	43	43 ± 14 days	[29, 57]
Week 12	85	85 ± 14 days	[71, 99]
Week 18	127	127 ± 14 days	[113, 141]
Week 24	169	169 ± 14 days	[155, 183]
Week 36	253	253 ± 21 days	[232, 274]
Week 48	337	337 ± 21 days	[316, 358]

For safety endpoints such as vital signs, laboratory tests, PVR, and ECGs, data records will be slotted to one of the protocol specified visits using the analysis visit window rules below:

After all the records have been assigned to an analysis visit, if there are more than one records in the same analysis visit, the one closest to the target day will be used (for records in screening and randomization visits, the later one will be selected). If equal distance, the earlier one will be used. If there are more than one results in the same day, the time portion of the collection date and time, the “repeat” status, or the inherent sequence in the electronic data capture (EDC) system will be used for differentiation and the later one will be used.

Table 3: Analysis Visit Window Slotting

Analysis Window Label	Nominal Visit	Nominal Day	Visit Window
Screening	Screening Visit	Not Applicable	Not Applicable
Randomization	Randomization Visit	Not Applicable	Not Applicable
Day 1	Day 1	1	Not Applicable
Week 2	Week 2	15	VS, PVR: [2, 29] ECG: [2, 50]
Week 6	Week 6	43	VS, PVR: [30, 64] Lab: [1, 106]
Week 12	Week 12	85	VS, PVR: [65, 106] ECG: [51, 127]
Week 18	Week 18	127	VS, PVR: [107, 148]
Week 24	Week 24	169	VS, PVR: 149+ ECG: 128+ Lab: 107+

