### 8.4.4. Post-Void Residual Volume

The volume of urine that remains in the bladder after voiding (PVR) is an objective measurement that may serve as a proxy for impaired ability to void. The physician should assess subjects with an increase in PVR volume to determine whether an AE should be reported. (Refer to [Section 8.5.6](#) for additional information on reporting AEs of urinary retention associated with increased PVR.)

The PVR assessment will be performed via ultrasound at the visits indicated in the Schedule of Assessments (Section 1.3). Note that since Visit 7 (Week 18) is a telephone (or other virtual technology) visit, subjects will not be seen in the clinic for 12 weeks between Visit 6 (Week 12) and Visit 8 (Week 24). Should the investigator identify a clinically relevant elevation in PVR volume at Visit 6, an unscheduled clinic visit should be performed at the investigator's discretion to repeat the urine PVR assessments and urine dipstick. All efforts should be made to ensure the same device and operator are used for all PVR volume measurements for individual subjects.

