##### *Initiation of Clean Intermittent Catheterization*

As described above in the PVR section, CIC should be initiated per protocol when one of the following criteria is fulfilled:

- PVR is  $\geq 350$  mL at any posttreatment visit, regardless of whether the subject reports associated symptoms
- PVR is  $\geq 200$  mL and  $< 350$  mL and the subject spontaneously reports associated symptoms (ie, voiding difficulties, sensation of bladder fullness) that in the opinion of the investigator requires CIC.

The following will occur when initiating CIC (for elevated PVR as described above):

1. CIC is implemented and the subject should be instructed to perform CIC using sterile, single-use catheters (which will be provided to the subject)
2. An adverse event of urinary retention is recorded
3. Central laboratory urine analysis and culture/sensitivity are performed as per routine requirements at each study visit
4. The subject will be seen for a follow-up visit 1 week later where the PVR, associated symptoms, central laboratory urine analysis and culture/sensitivity will be reassessed. The investigator will determine whether the subject can then be followed per protocol scheduled study visits or whether additional follow-up visits should occur.

Once CIC is initiated, the status of CIC use should be documented in the subject record at each visit (ie, use/nonuse).

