#### **8.4.6. Clinical Safety Laboratory Assessments**

All protocol-defined laboratory assessments must be conducted in accordance with the laboratory manual and the Schedule of Assessments ([Section 1.3](#)). See [Section 10.2](#) for the list of clinical laboratory tests to be performed and the Schedule of Assessments for the timing and frequency. Repeat or unscheduled samples may be taken for safety reasons or for technical issues with the samples.

The clinical significance of test results will be evaluated as follows:

- At screening, the investigator or physician subinvestigator will assess the clinical significance of any values outside the reference ranges provided by the laboratory, and subjects with abnormalities judged to be clinically significant will be excluded from the study.
- The investigator or physician subinvestigator must review the laboratory report, document this review, and record any clinically relevant changes occurring during the study in the AE section of the eCRF. The laboratory reports must be filed with the source documents. Laboratory abnormalities associated with the underlying disease are not considered clinically significant unless judged by the investigator to have worsened or be more severe than expected for the subject's condition.
- All laboratory tests with values considered clinically significant during participation in the study should be repeated until the values return to normal or baseline or are no longer considered clinically significant by the investigator or Sponsor's designated Medical Monitor.
  - If such values do not return to normal/baseline within a period of time judged reasonable by the investigator, the etiology should be identified and the Sponsor's designated Medical Monitor notified.
  - If laboratory values from nonprotocol specified laboratory assessments performed at the institution's local laboratory require a change in subject management or are considered clinically significant by the investigator (eg, SAE or AE or dose modification), then the results must be recorded in the eCRF.

A urine dipstick will be performed at the study site at scheduled visits as noted in the Schedule of Assessments ([Section 1.3](#)) and when a subject presents with symptoms of a UTI at Unscheduled

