4.2.2. Reporting Conventions

General rules

In general, all collected safety data, any derived efficacy parameters from the bladder diary, questionnaire data, and urodynamic data will be presented in subject data listings. Listings will be ordered by treatment, subject number, and assessment week or event date. The treatment group presented in listings will be based on the planned assignment for efficacy endpoints and actual assignment for safety endpoints.

Summary tables will be provided for all randomized subjects. All demographic and baseline data will be presented by treatment arm and overall, unless otherwise specified. Bladder diary, questionnaire, urodynamic data, and safety data will be presented by treatment arm only. In general, continuous variables will be summarized to include the population sample size (N), number of subjects with available data (n), arithmetic mean, standard deviation (SD), median, minimum, Q1, Q3 and maximum values. Categorical variables will be summarized by the population size (N), number of subjects with available data (n), number of subjects in each category, and the percentage of subjects in each category. Unless otherwise noted, the denominator to determine the percentage of subjects in each category will be based on the number of subjects with available data (n) in the analysis set of interest. Selective ordinal data may be summarized using both descriptive statistics as well as counts and percentages of subjects in each category, as appropriate.

The data analyses will be conducted using the SAS® System (SAS Institute Inc., Cary, NC) version 9.3 or above. The eClinical Solutions' standard operating procedures will be followed for the validation of all SAS programs and outputs.

Formats

Numeric data will be reported at the precision collected on the electronic case report form (eCRF). The reported precision from non eCRF sources may be adjusted to a clinically interpretable number or decimal places.

Unscheduled Visits

Unscheduled visits will be assigned to an analysis visit using the all-inclusive windows defined in [Section 4.2.4](#). If multiple assessments are done in the same visit, the selection rule in [Section 4.2.4](#) will apply. All assessments at unscheduled visits will be included for deriving last post-baseline or maximum value post-baseline and in the data listings.

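### By-visit safety tables give the scheduled record no priority over a recheck prompted by an abnormal value, and PVR and vital signs have a Week 18 window with no planned measurement behind it

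*SAP*

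**What the plan says.** SAP 4.2.4 sets the scope of the windows: "For safety endpoints such as vital signs, laboratory tests, PVR, and ECGs, data records will be slotted to one of the protocol specified visits". SAP 4.2.2 brings unplanned records in: "Unscheduled visits will be assigned to an analysis visit using the all-inclusive windows defined in" Section 4.2.4, and the selection rule there applies to them. That rule has three parts:

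- Several records in one window: "if there are more than one records in the same analysis visit, the one closest to the target day will be used".
- Ties: "If equal distance, the earlier one will be used".
- Several results on one day: time, repeat status or database sequence "will be used for differentiation and the later one will be used".

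Nothing in the rule prefers the scheduled record.

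The protocol produces extra records in response to abnormal results:

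- Section 8.4.4: after a raised Week 12 PVR that the investigator considers relevant, an unscheduled visit at the investigator's "discretion to repeat the urine PVR assessments and urine dipstick".
- Section 8.4.5: once clean intermittent catheterization (CIC) begins, "The subject will be seen for a follow-up visit 1 week later where the PVR, associated symptoms" and urine tests are reassessed. A similar 1-week visit follows when CIC stops.
- Section 8.4.6: clinically significant laboratory results "should be repeated until the values return to normal or baseline", or until they are no longer judged significant.

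SAP Table 3 gives vital signs and PVR a Week 18 window of Days 107-148. The Schedule of Assessments plans neither at Week 18, Protocol 8.4.4 says subjects are not seen in clinic then, and SAP 7.4 says vital signs are not collected at telephone visits. The ECG and laboratory windows in the same table skip the visits at which those tests are not planned.

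**The concern.** Whether a subject has a second record in a window depends partly on whether the first was abnormal. If that second record can take the place of the first, the by-visit summaries are chosen in a way linked to the outcome. The outputs exposed are the by-visit PVR summary (Table 14.3.7, a topline deliverable) and the counts of out-of-range laboratory values by visit (Tables 14.3.3.2 and 14.3.3.5). PVR is the study's measure of impaired voiding, so its time course by arm will be read closely.

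The Week 18 window raises a separate problem. A row with no planned measurement is a selected subset, yet it would sit in the table beside rows that describe nearly the whole arm.

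**Working it through.** **Inputs.** Target days 15, 43, 85, 127 and 169 (SAP Table 3). Visit windows of ±3 days at Week 2 and ±7 days at Weeks 6, 12 and 24, with a COVID-19 alternative of +4 weeks at Weeks 6, 12 and 24 (Schedule of Assessments). CIC recheck lag of 7 days (Protocol 8.4.5). Planned arm size of 26 per dose.

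**Reproducing Table 3.** Each upper bound is the midpoint of consecutive target days.

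- PVR and vital signs: (15+43)/2 = 29, (43+85)/2 = 64, (85+127)/2 = 106, (127+169)/2 = 148.
- ECG: (15+85)/2 = 50, (85+169)/2 = 127.
- Laboratory: (43+169)/2 = 106.

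All agree with the SAP.

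**When a recheck displaces the scheduled value.** Let the visit be e days before target and the recheck L days after the visit. The recheck is kept when |L − e| < e, that is, when L < 2e. A visit on or after target is never displaced by a later-day recheck. At L = 2e the tie rule keeps the earlier record. Permitted visit days on which displacement occurs:

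| Lag L (days) | Weeks 6, 12, 24 (of 15 days) | Week 2 (of 7 days) |
|---|---|---|
| 1 | 7 | 3 |
| 3 | 6 | 2 |
| 5 | 5 | 1 |
| 7 | 4 | 0 |
| 10 | 2 | 0 |
| 13 | 1 | 0 |
| 14 or more | 0 | 0 |

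The ±7-day column applies to PVR at Weeks 6, 12 and 24 and to laboratory tests at Weeks 6 and 24. At L = 7, e must be 4, 5, 6 or 7, giving 4/15 = 27% of permitted days. Example: a PVR of 350 mL or more on Day 78 starts CIC, and the Day 85 recheck becomes the Week 12 value. A same-day repeat displaces the first result whatever the visit day.

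**Effect on a mean.** The documents give no recheck values. If one of 26 subjects (1/26 = 3.8%) is displaced and the recheck is lower by 100 to 300 mL (assumed), the arm mean falls by 100/26 = 3.8 mL to 300/26 = 11.5 mL. A higher recheck raises it by the same arithmetic.

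**Week 18.** A Week 12 visit on Days 78-92 with a 1-week recheck puts the recheck on Days 85-99, inside the Week 12 window of Days 65-106. Reaching Day 107 needs a lag of 107−92 = 15 to 107−78 = 29 days. Early-withdrawal exit assessments (Protocol 7.1) can also fall on Days 107-148. Under the COVID-19 window a Week 12 visit may be as late as 85+28 = Day 113, so on Days 107-113 its PVR and vital signs are labelled Week 18 and leave the Week 12 row. Likewise a Week 6 visit may be as late as 43+28 = Day 71, and on Days 65-71 it is slotted to Week 12.

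**Does SAP 7.7 already prevent this?** It speaks of scheduled visits for the by-visit PVR summary, but exempts only the maximum and last values from the window rules. The natural reading is that the by-visit values do use them.

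**The case against.** The selection rule is pre-specified and does not look at the value: an unscheduled high reading nearer the target would replace a lower scheduled one just as readily. The 27% is a share of calendar days. It applies only to subjects who have a recheck, and over the union of the standard and COVID-19 windows (−7 to +28, 36 days) it is 4/36 = 11%. Protocol 2.3.2 reports no urinary retention in earlier work at doses up to 24 mg. If one or two subjects in 26 started CIC (an assumption) and all 15 days were equally likely, about 0.3 to 0.5 scheduled values per arm would be displaced.

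Retention is also captured elsewhere. Maximum and last PVR ignore the windows (SAP 7.7). Laboratory shifts go to the maximum, minimum and last value (SAP 7.3). Retention needing catheterization is an adverse event of special interest (Table 14.3.1.11), and CIC has its own table (14.3.8). All records are listed, and SAP 7 plans no inferential safety testing.

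All of this stands and limits the point to the by-visit rows. It does not remove it, because those rows are planned outputs. Two gaps also remain in the safeguards. SAP 7.7 does not say whether the PVR categories, whose cut-offs include 200 and 350 mL, are tabulated by visit or on the maximum. SAP 4.2.2 admits unscheduled values to the last and maximum derivations but does not name the minimum.

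**Conclusion.** The point holds for the descriptive by-visit safety summaries. With no priority for the scheduled record, and with rechecks prompted by abnormal values, a recheck can replace the value that prompted it, and by-visit PVR and abnormal-laboratory summaries can be biased. For a 7-day recheck this needs a Week 6, 12 or 24 visit 4 to 7 days early. No frequency can be predicted, because the documents give no distribution of visit timing or recheck lag. The rule also covers vital signs and ECG, but the protocol passages cited here tie rechecks to abnormal results only for PVR and laboratory tests.

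The Week 18 window for PVR and vital signs conflicts with the schedule. Any row it yields can hold only unplanned, early-withdrawal or delayed measurements.

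A reader might infer more, and the documents do not support it:

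- That the Week 18 row would consist mainly of subjects recalled for high PVR and show a spike. Other sources feed the same days, the 1-week CIC recheck after an in-window Week 12 visit stays in Week 12, and the reference to scheduled visits in SAP 7.7 leaves it unclear whether the row will be printed.
- That PVR is understated in the arm where retention occurs. Nothing shows that rechecks are systematically lower.
- That the by-visit results are wrong. They can be biased, and companion outputs retain the event.

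**What to change.** In SAP 4.2.2 and 4.2.4:

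- For by-visit summaries of PVR, vital signs, ECG and laboratory tests, use the scheduled (nominal-visit) record when it exists. Use an unscheduled record in the window only when the scheduled one is missing. Displacement then falls to 0 of 15 days at every lag, same-day repeats no longer displace the scheduled result, and COVID-delayed visits keep their proper label. Do not bar rechecks from filling a missing visit: that would make the visit missing selectively for subjects with abnormal results and would need the reason for each test.
- State that early-withdrawal exit records are still slotted by study day, since a nominal rule alone would call them Week 24.
- Remove Week 18 from the vital-sign and PVR windows and redraw by the midpoint rule: (85+169)/2 = 127, so Week 12 becomes Days 65-127 and Week 24 Day 128 onward. The Day 127/128 boundary is the one Table 3 already uses for ECG.
- Keep all unscheduled values in the maximum, minimum and last derivations and in listings, naming the minimum explicitly.
- In SAP 7.7, state that the PVR category summary is also given on the maximum post-baseline value.

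The cost is SAP wording and record-selection code, with no new data. By-visit PVR and abnormal-laboratory figures may look slightly less favourable.

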4.3. Data Definitions and Deviations

4.3.1. Efficacy Data Collection Schedule

Efficacy assessments will be collected as outlined in [Table 4](#) below. Refer to protocol section 1.3 (Schedule of Assessments) for the details on the day of visit and timing of measurement.

Table 4: Efficacy Assessments

Assessment	Form	Measurement and Timing
Bladder Diary	Bladder Diary – Day 1 Bladder Diary – Day 2 Bladder Diary – Day 3 eCRF form	For any 3 consecutive days within the Screening and Randomization period (Visits 1 and 2) and any 3 consecutive days in the 7 days prior to the clinical visit (Weeks 2, 6, 12, 18, 24, 36, and 48 (Visits 4-10, respectively)), subjects will record daily urination data including “Need to urinate immediately” “Urinated in toilet” “Accidental urine leakage” “Main reason for leakage” For one 24-hour period, subject will also record the urine volume for one of the diary days

Assessment	Form	Measurement and Timing
Health Outcome parameters	
 • Incontinence Quality of Life Instrument (I-QOL) eCRF • Overactive Bladder Questionnaire (OAB-q) eCRF • Patient Global Impression of Change Scale (PGI-C) eCRF 	
 • I-QOL: Day 1, Weeks 6, 12 • OAB-q: Day 1, Weeks 6, 12 • PGI-C: Week 12
Urodynamics	Urodynamics – Site Urodynamics – Central Reader	Prior to Randomization at Visit 2 and Week 12

4.3.2. Bladder Diary Data

Bladder Diary data are collected following the schedule of assessments in Section 1.3 of the protocol. Per protocol diaries will not be collected if subjects receive additional OAB treatment(s) at Week 24 or after. For summary and analysis purpose, any bladder diaries collected after the first additional OAB treatment will not be included in defining the subsequent endpoints based on the bladder diaries. All bladder diaries collected will be included in the listings.

4.3.2.1. Average Daily Number of UUI Episodes

Average daily number of UUI episodes is calculated as the total number of UUI episodes recorded on the bladder diary days that fall within the visit window divided by the number of days the Bladder Diary is filled out. A UUI episode is defined as when a subject checked “Urge” to the question “select main reason for leakage” on the bladder diary eCRF. Subjects may have more than one bladder diary filled out on the same day and all the UUI episodes will be summed together. The denominator used for calculating the average number will only count the days in which there is a completed bladder diary day within the visit window.

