#### **9.4.1. Efficacy, Health Outcome, and Urodynamics Endpoints**

For the purposes of this study, the number of UUI episodes will be defined as the number of times a subject has marked “urge” as the main reason for the leakage as indicated on the Bladder Diary; regardless of whether more than one reason for leakage in addition to “urge” is checked. Average daily number of UUI episodes is calculated using the daily entries in the Bladder Diary, which is completed prior to each study visit. Average daily number of UUI episodes will be calculated as the total number of UUI episodes that occur on a Diary Day divided by the number of Diary Days in the Bladder Diary.

A micturition is defined as “Urinated in Toilet” as indicated on the Bladder Diary. Average daily micturitions at each study visit will be calculated in the same manner as described above for UUI episodes.

Urinary incontinence is defined as having any reason for leakage or “Accidental Urine Leakage” as indicated on the Bladder Diary.

An urgency episode is defined as the “Need to Urinate Immediately” as indicated on the Bladder Diary.

Exploratory Efficacy Endpoints are listed in [Section 3.2.1](#).

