4.3.2.2. Average Daily Number of Micturitions

Average daily number of micturitions is defined as the total number of times a subject checked “Urinated in toilet” or recorded non-zero urine volume in a completed bladder diary day within the visit window divided by the number of days the Bladder Diary is filled out. Subjects may have more than one bladder diary filled out on the same day and all the micturitions will be summed together. The denominator used for calculating the average number will only count the days in which there is a completed bladder diary day within the visit window.

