4.3.2.3. Average Daily Number of UI Episodes

Average daily number of UI episodes is calculated as the total number of UI episodes recorded on a completed diary day within the visit window divided by the number of days the Bladder Diary is filled out. A UI episode is defined as when a subject answered “Yes” to the question “Accidental urine leakage” or indicates any reason for leakage on the bladder diary eCRF.

Subjects may have more than one bladder diary filled out on the same day and all the UI episodes will be summed together. The denominator used for calculating the average number will only count the days in which there is at least one completed bladder diary day within the visit window.

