4.3.2.4. Average Daily Number of Urgency Episodes

Average daily number of urgency episodes is calculated as the total number of urgency episodes recorded on a completed diary day within the visit window divided by the number of days the Bladder Diary is filled out. An urgency episode is defined as when a subject answered “Yes” to the question “Need to urinate immediately” on the bladder diary eCRF. Subjects may have more than one bladder diary filled out on the same day and all the urgency episodes will be summed together. The denominator used for calculating the average number will only count the days in which there is at least one completed bladder diary day within the visit window.

4.3.2.5. Proportion of Subjects Achieving $\geq 50\%$, $\geq 75\%$, and 100% Reduction from Baseline at Week 12 in UUI Episodes per Day

Proportion of subjects achieving x% reduction from baseline is defined as: - (Average daily number of UUI episodes at Week n – UUI at Baseline) / UUI at Baseline * 100%. This is defined when both baseline and post-baseline average daily number of UUI episodes are non-missing. For responder analyses, missing reduction from baseline will be considered non-responders for the visit in question.

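### Read literally, the SAP's UUI average counts episodes from every diary day in the window but divides by completed days only, so a part-filled post-baseline day raises the average and lowers the UUI responder rates

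*SAP*

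**What the plan says.** SAP 4.3.2.1 builds the UUI average from three statements:

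- The numerator is the "total number of UUI episodes recorded on the bladder diary days that fall within the visit window". No completeness condition is attached.
- The total is "divided by the number of days the Bladder Diary is filled out".
- The closing sentence says that the denominator "will only count the days in which there is a completed bladder diary day within the visit window".

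The neighbouring definitions put the completeness condition on the numerator as well. UI (4.3.2.3) uses the "total number of UI episodes recorded on a completed diary day within the visit window" and urgency (4.3.2.4) uses the "total number of urgency episodes recorded on a completed diary day within the visit window". Micturitions (4.3.2.2) counts a toilet void or "recorded non-zero urine volume in a completed bladder diary day within the visit window", and nighttime voids (4.3.2.7) follows the micturition wording. UUI alone lacks the condition.

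Protocol 9.4.1 defines the same average as the "total number of UUI episodes that occur on a Diary Day divided by the number of Diary Days in the Bladder Diary", with one set of days above and below the line. SAP section 9, which lists changes from the protocol's analysis, does not mention this difference.

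**The concern.** If the two parts of the ratio cover different days, the result is not a daily average. Every episode on a part-filled day goes into the total, and the day itself is left out of the divisor.

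Change in UUI is the first-listed efficacy endpoint and the one used in the sample-size statement (SAP 1.2.4). The ≥50%, ≥75% and 100% responder endpoints are percent reductions computed from the same average (SAP 4.3.2.5), so an error in the average can move a subject across a responder threshold.

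The rule can also give an impossible result. Any leak with a stated reason counts as UI (SAP 4.3.2.3), so every UUI episode is a UI episode. Yet a subject's UUI average could exceed her UI average at the same visit, because only the UI numerator drops part-filled days.

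**Working it through.** **The plan's own figure.** SAP 1.2.4 gives 23 evaluable subjects per group, a difference of 1.8 episodes per day, SD 2.86 and two-sided 0.05. The standard error is 2.86 × √(2/23) = 0.843 and the noncentrality is 1.8/0.843 = 2.13 on 44 degrees of freedom. Power from the noncentral t distribution is 55.1%, which matches the stated 55%. The sizing is not in dispute; it shows only which endpoint the definition feeds.

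**Formula.** Let k be the number of completed days in the window, C the UUI episodes on them, and P the UUI episodes on part-filled days.

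- Literal rule: (C + P)/k
- Completed days in both parts: C/k
- Excess of the literal rule: P/k, which is never negative

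Percent reduction (SAP 4.3.2.5) is (baseline − post)/baseline × 100, so a higher post-baseline average gives a smaller reduction.

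**Illustrations.** These diaries are assumed, because the documents give no data on part-filled days. Baseline is 4.0 per day. The last column shows what follows if the part-filled day is counted in both parts.

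| Week 12 diary | Literal rule | Completed days in both parts | All days in both parts |
|---|---|---|---|
| 2, 2, 2 completed; 1 on a part-filled day | 7/3 = 2.33; 41.7% | 6/3 = 2.0; 50% | 7/4 = 1.75; 56.3% |
| 2, 2 completed; 1 part-filled | 5/2 = 2.5; 37.5% | 4/2 = 2.0; 50% | 5/3 = 1.67; 58.3% |
| 1, 1 completed; 1 part-filled | 3/2 = 1.5; 62.5% | 2/2 = 1.0; 75% | 3/3 = 1.0; 75% |
| 0, 0 completed; 1 part-filled | 1/2 = 0.5; 87.5% | 0; 100% | 1/3 = 0.33; 91.7% |

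Compared with the completed-day rule, the literal rule costs the subject ≥50% status in rows 1 and 2, ≥75% status in row 3 and 100% status in row 4. In row 1, if all leaks are urge leaks, her UI average is 2.0 and her UUI average is 2.33.

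Row 1 needs a fourth diary day in the window. The protocol asks for three days per visit, so this is an assumption, but the Week 12 diary window runs from day 71 to day 99 (SAP 4.2.4), which is 99 − 71 + 1 = 29 days. Rows 2 to 4 have only two completed days, so they arise only if the three-day rule in SAP 4.3.5 does not bind post-baseline visits.

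**Reverse case.** Suppose one of the baseline days is part-filled: completed days of 4 and 4 and a part-filled day with 2. The literal baseline is 10/2 = 5.0 instead of 4.0. With Week 12 at 2.2 per day, the reduction is 2.8/5.0 = 56% instead of 1.8/4.0 = 45%.

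**Order of magnitude.** A simulation assumed Poisson daily counts, two completed days plus one part-filled day for affected subjects, half of that day's episodes recorded, and 5% to 30% of subjects affected after baseline.

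| Subjects affected | Mean change, literal | Mean change, completed days | ≥50% responders, literal | ≥50% responders, completed days |
|---|---|---|---|---|
| 5% | −1.787 | −1.814 | 60.6% | 60.9% |
| 30% | −1.651 | −1.816 | 59.0% | 61.1% |

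The apparent improvement shrinks by 0.03 to 0.17 episodes per day, and the ≥50% responder rate falls by about 0.3 to 2 percentage points.

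**The case against.** The strongest reply is that the mismatch depends on how *completed* is read. Neither document defines it or *filled out*, and the documents also use *completed* simply to mean that a diary was kept. The denominator sentence comes straight after the remark about several diaries on one day, so it could mean only that each diary day is counted once and days without a diary are not counted. On that reading both parts cover the same days. This is possible, but it does not explain why UUI alone lacks a condition that four sibling definitions carry. Two programmers could reasonably produce different UUI datasets.

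A second reply is that SAP 4.3.5 requires all three diary days for the change from baseline. If that applies after baseline, a visit with two completed days is missing and is scored as a non-responder whichever numerator is used. The sentence sits in the baseline paragraph and its reach is unclear. If it does apply, only the case with an extra part-filled day in the window remains. SAP 4.2.4 has a rule for choosing one record per visit, but it follows the paragraph on safety data, whereas 4.3.2.1 sums over days.

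Third, Protocol 9.4.1 does not establish completed days as the right basis. The Diary Day in Protocol 8.2.1 has no completeness test, so counting every day in both parts would also fit it. This stands: the protocol supports matching days, and the case for *completed* comes from the SAP's own sibling definitions.

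Finally, Protocol 8.2.1 has subjects confirm each morning that all events were entered, which should limit part-filled days.

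**Conclusion.** The literal rule in SAP 4.3.2.1 puts different days above and below the line, for UUI only, and looks like a drafting slip. A part-filled post-baseline day with at least one UUI episode raises the average by P/k, makes the change from baseline look smaller and can only lower responder rates.

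Three stronger readings are tempting and are not supported:

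- A reader might infer that the rule inflates responder rates. It does so only if the part-filled day is at baseline. Protocol 8.2.1 requires three consecutive Diary Days for entry and SAP 4.3.5 requires all three, which makes that less likely.
- A reader might infer a bias in favour of one arm. Nothing in the documents shows that part-filled days would be more common in either arm.
- A reader might treat this as a flaw in a primary endpoint. The study has no formal primary endpoint; UUI change is first-listed and used for sizing.

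The overall size cannot be derived from the documents. On the assumed inputs above it is modest: at most about 0.17 episodes per day, against a planning SD of 2.86. For a single subject near a threshold it can decide responder status, in groups of about 23 evaluable subjects.

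**What to change.** In SAP 4.3.2.1, restrict the UUI numerator to episodes recorded on completed diary days in the window, so that it covers the same days as the denominator and matches 4.3.2.2 to 4.3.2.4 and 4.3.2.7. In the same revision:

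- define a completed diary day, and use that one term in place of *filled out*;
- state whether the three-day rule in SAP 4.3.5 applies to post-baseline visits;
- add a programming check that the UUI average does not exceed the UI average at any subject-visit.

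The core change is one phrase. The rest is a definition, a sentence and a check, and no new data are needed.
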